## 6.2 Clinical and Pharmacokinetic Studies

The Investigator's Brochure (IB) contains detailed information on clinical and non-clinical studies. Results of the Phase 3 MAL cream DL-PDT studies are summarized below. A PK study has been recently conducted in the United States.

### 6.2.1 Phase 3 MAL cream DL-PDT studies

The efficacy and safety of MAL 16.8% cream DL-PDT were compared with MAL 16.8% cream c-PDT in 2 randomized, investigator-blinded, comparative, intra-individual clinical studies conducted in Australia and Europe, in 231 subjects. Subjects were treated on 1 side of the face or scalp with MAL 16.8% cream DL-PDT and on the contralateral side with MAL 16.8% cream c-PDT.

The results of both Phase 3 studies demonstrated that the efficacy of MAL 16.8% cream DL-PDT is similar (noninferior) to MAL 16.8% cream c-PDT for treatment of AK lesions (on the percentage change from Baseline in the number of treated lesions per side at 12 weeks after 1 treatment), and is significantly less painful.

In the Australian study, the percentage change from Baseline in the number of mild treated lesions was 89.2% for DL-PDT versus 92.8% for c-PDT (95% confidence interval [CI] of the mean treatment difference: [-6.8; -0.3], PP population). In the European study, the percentage change from Baseline in the number of total (mild and moderate) treated lesions was 70.1% for DL-PDT versus 73.6% for c-PDT (95% CI of the mean treatment difference: [-9.5; 2.4], PP population).

Methyl aminolevulinate hydrochloride 16.8% cream DL-PDT was almost painless compared with MAL 16.8% cream c-PDT, with a pain score (on an 11-point scale ranging from 0 to 10) of 0.8 versus 5.7 ( $p<0.001$ ) in the Australian study, and 0.7 versus 4.4 ( $p<0.001$ ) in the European study.

In both studies, regardless of whether the weather was sunny or cloudy, similar efficacy was demonstrated.

The maintenance of lesion response rate assessed in the Australian study was high with both treatments for subjects presenting at Week 24 (96% for DL-PDT lesions and 96.6% for c-PDT lesions).

In these two Phase 3 studies, in 231 subjects, local related adverse events (AEs) were reported less frequently on MAL cream DL-PDT than on MAL cream c-PDT treated sides (45.0% and 60.1% of subjects, respectively).

No new local adverse reactions were reported in the 2 MAL DL-PDT Phase 3 studies compared with the already known local adverse reactions with MAL c-PDT. Methyl aminolevulinate hydrochloride DL-PDT was almost painless compared with MAL c-PDT.

### 6.2.2 PK Study (MUsT)

The PK profiles of MAL and its metabolites, ALA and PpIX, were assessed in 23 subjects with AK lesions following two topical applications at least 2 weeks apart, of the to-be marketed formulation under maximal use conditions. The study was an open-label study of adult men and women with at least 10 mild to moderate actinic keratosis of the face or balding scalp.

The purpose of this maximal use trial (MUsT) was to assess systemic exposure at the upper range of disease severity of the population that will be enrolled in the proposed pivotal phase 3 study [RD.06.SPR.112199]. The mean number of treated lesions reported in the MUsT (i.e.,  $N=14.5 \pm 6.56$  lesions, range 10 to 30 AK lesions) exceed the maximum number of lesions that will be treated in the Phase 3 study (i.e.,  $N=12$  lesions)

Subjects received two separate single-dose applications of MAL cream on the face or on the balding scalp with a 2-week washout period between the two applications. A total of 24 adult subjects with AK lesions on the face or balding scalp received lesion-directed treatment, and then had 2 hours of daylight under 3 different conditions: full shade, full sunlight, and full sunlight with physical exercise.

After two topical application of MAL cream, the systemic exposure to the unchanged compound (MAL) was very low, i.e. no more than 3 times the LOQ (2 ng/mL) and transient in time with MAL systemic exposure limited to no more than a 3-hour duration after the first treatment only. Given the limited systemic exposure of MAL and its quick methyl ester hydrolysis in its acid form ALA, no drug accumulation is expected and hence the parent drug potential for systemic toxicity or drug-drug interaction is unlikely.

The two MAL metabolites, ALA and PpIX, are endogenous substances and exogenous application of MAL cream on lesions resulted in a non-significant increase of ALA systemic exposure and in a negligible increase of PpIX systemic exposure (up to a maximum of 34% of the 24-hour PpIX endogenous level).

Of note, the increase in PpIX exposure from baseline and presence of quantifiable MAL concentrations were observed mainly in subjects presenting with a number of AK lesions (at least 30) that greatly exceed the maximum number of AK lesions that will be treated in the proposed Phase 3 study.

There were no clinically significant changes in ECG findings, nor changes in tolerability or new types of AEs found in the study.

### 6.3 Risk/Benefit Assessment

Metvix® cream (methyl aminolevulinate 16.8%) is currently marketed worldwide by Galderma for the treatment of thin or non-hyperkeratotic and non-pigmented AK of the face and scalp, and in some countries for the treatment of superficial and nodular BCC and the treatment of SCC *in situ* (Bowen's disease) in adults.

The cumulative post-marketing patient exposure to MAL cream is estimated to be 2,213,42 patient treatments, calculated on the basis of number of tubes sold worldwide and the assumption that a single 2-g tube is used for 2 patient treatments. In the near future, the 2-g tube will be a unidose tube, intended for one use only.

Galderma has developed a new treatment regimen of the product in which DL is used in place of the previously authorized red light-emitting diode (LED) for the illumination in the treatment of AKs. This has been approved in various countries and Galderma is now developing methyl aminolevulinic acid cream 16.8% (CD06809-41) DL-PDT in the United States for the treatment of AK.

With regards to safety, in clinical studies conducted with MAL c-PDT in subjects with AKs, BCC, or Bowen's disease, approximately 60% of subjects experienced reactions localized to the treatment site, attributable to toxic effects of the photodynamic therapy (phototoxicity) or to preparation of the lesion. The most frequent symptoms were painful and burning skin sensation, typically beginning during illumination or soon after and lasting for a few hours with resolution on the day of treatment. The symptoms were usually of mild or moderate severity and rarely required early termination of illumination. The most frequent signs of phototoxicity were erythema and scab. The majority were of mild or moderate severity and persisted for 1 to 2 weeks, or occasionally longer. Repeated treatment with Metvix was associated with a reduced frequency and severity of local phototoxic reactions.

In the post-marketing experience, the following adverse drug reactions were the more relevant ones reported with Metvix cream: eyelid edema, angioedema, face edema (swelling face), application site eczema, allergic contact dermatitis, and rash pustular (application site pustule). In addition, hypertension and transient global amnesia were reported with Metvix cream used with c-PDT (refer to the Investigators' Brochure).

In the two Phase 3 MAL DL-PDT studies conducted in subjects with AKs to compare MAL DL-PDT with MAL c-PDT, no new local adverse reactions were reported compared with the already known local adverse reactions with MAL c-PDT. Methyl aminolevulinate hydrochloride DL-PDT was almost painless compared with MAL c-PDT.

As a conservative approach, the calculation presented below considers the treatment conditions expected to maximize the MAL hydrochloride 16.8% cream (CD06809-41) penetration, i.e., the field treatment after preparation of the lesional skin with a pad (sterile gauze).

The *in vitro* total penetration through the skin of MAL 16.8% cream (CD06809-41) in humans, after a 2.5-hour contact on skin pretreated with preparation pad (sterile gauze), corresponded to up to 6.853% of the applied dose after 10 passages with the preparation pad (study RDS.03.SRE.105070). Thus, after an administration of 2 g of CD06809-41 cream, a theoretical maximum up to 23.03 mg of MAL could be absorbed systematically (336 mg x 6.85/100), which would represent 0.46 mg/kg for a 50 kg subject (23.03 mg/50 kg). Using a conversion factor of 37 for humans, the maximum recommended human dose (MRHD) for each application is 17.02 mg/m^2 (0.46 x 37).

For comparison, the MUSt PK study RD.06.SPR.108431, performed in subjects with mild to moderate AKs, demonstrated that between 0.11 and 0.54 g of MAL cream was sufficient to cover between 10 and 37 AKs on skin surface area, measuring between 12 and 67 cm^2. After cream administration, the systemic MAL exposure was mainly non-quantifiable, with few subjects having very low MAL plasma concentrations (Cmax between 2.14 and 6.19 ng/mL) limited to about 3 hours after the first treatment. Therefore, the safety profile of MAL 16.8% cream can be considered well established.

All nonclinical animal studies were performed with the MAL-HCl salt, and consequently, NOAEL expressed as MAL are to be divided by a 1.251-fold factor, as MAL-HCl has a formula weight of 181.62 g and MAL of 145.17 (difference for HCl of 35.45 g).

The safety margins based on the NOAELs at MAL 160 mg/kg/day (200 mg/kg/day MAL-HCl), determined based on systemic toxicity (liver cholangitis/pericholangitis) after IV administration in rats for 2 weeks and on the NOAELs based on reproduction toxicity studies are summarized in Table 2. These safety margins consider comparisons on an mg/m^2 basis with the maximum recommended human dose (MRHD) for each application being 17.02 mg/m^2. The conversion factor for rats is 6 and it is 12 for rabbits. With this method of

calculation, the lowest estimated safety margin for the study is 35 (based on pre/postnatal toxicity in a rat study).

Therefore, based on the extensive pre- and post-marketing safety data available for the product, MAL cream remains effective and safe with a favorable benefit/risk ratio.

With regards to efficacy, MAL DL-PDT has been demonstrated to be as effective as MAL c-PDT for the treatment of AKs, and has already been approved in several countries for this indication.

Overall, the cumulative post-marketing experience, as well as the information from the clinical studies and literature, confirm that the benefit-risk ratio remains positive for the use of MAL in the approved indications in the various countries in which it is approved, and supports the conduct of the proposed study.

**Table 2: Safety Margins for MAL comparing NOAEL and MRHD expressed as mg/m^2**

| Study type
(Study number)               | Species | NOAEL
(expressed as MAL)                 | Safety margin
versus MRHD
(17.02mg/m  ) a |
|--|---------|---|--|
| 14-day IV administration
(1555/7-D6144) | Rat     | 160 mg/kg/day = 960 mg/m  /day  | 56   |
| Male and female fertility
(494190)      | Rat     | 400 mg/kg/day = 2400 mg/m  /day | 141  |
| Embryo-fetal development
(494054)       | Rat     | 280 mg/kg/day = 1680 mg/m  /day | 98   |
| Embryo-fetal development
(494080)       | Rabbit  | 80 mg/kg/day = 960 mg/m  /day   | 56   |
| Pre/postnatal toxicity
(494274)         | Rat     | 100 mg/kg/day = 600 mg/m  /day  | 35   |

a) conservative approach, assuming a human body weight of 50 kg and a 2 g application

#### 6.4 Drug Profile

Methyl aminolevulinate cream contains 16.8% of methyl aminolevulinate hydrochloride; each gram of cream contains 168 mg of MAL in a cream base. It is a patented derivative of ALA. Methyl aminolevulinate is not a photosensitizing agent itself, but its topical application results in the formation of photoreactive PpIX. Light activation of accumulated PpIX leads to a photochemical reaction and thereby, phototoxicity to the light-exposed target cells.

---

## 7 STUDY OBJECTIVES & ENDPOINTS

### 7.1 Primary Objective

The primary objective is to evaluate the safety and efficacy of MAL DL-PDT in adult subjects with mild to moderate actinic keratoses on the face and scalp over a 14-week period, and to show superiority in efficacy of MAL cream over vehicle cream at 12 weeks after the last DL-PDT session (Visit 6).

### 7.2 Secondary Objectives

- Compare the lesion response between MAL DL-PDT and vehicle DL-PDT
- Compare partial clearance of actinic keratoses (AKs) between MAL DL-PDT and vehicle DL-PDT
- Compare subject assessment of pain (by NRS) between MAL DL-PDT and vehicle DL-PDT
- Assess safety, including adverse events
- Document the estimated PpIX effective dose for each subject DL-PDT exposure through satellite image data

### 7.3 Primary Endpoint

The primary efficacy endpoint is the subject complete response, defined as the proportion of subjects with complete clearance of all AK lesions treated, at 12 weeks after the last DL-PDT (Visit 6), comparing MAL cream with vehicle cream.

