#### 8.3.2 Inclusion Criteria

To be eligible for study entry, subjects must satisfy all of the following inclusion criteria:

1. Male or female subjects age 18 years or older
2. Subjects have at least 4 but no more than 12 clinically confirmed thin and moderately thick (Grade I and II in the Olsen scale, respectively), non-hyperkeratotic, non-pigmented AK lesions located in on the face (e.g., forehead, cheek, chin), and balding scalp (excluding eyelids, lips and mucosa)
3. A: Female subjects of non-childbearing potential: postmenopausal (absence of menstrual bleeding for 1 year prior to Screening, without any other medical reason), hysterectomy or bilateral oophorectomy.  
B: Female subjects of child-bearing potential: negative urine pregnancy tests at Screening and Baseline visits. Female subjects of childbearing potential must agree either to be strictly abstinent until one completed menstrual cycle after the last DL-PDT, or to use an effective and approved method of contraception until one completed menstrual cycle after the last DL-PDT. This criterion also applies to a prepubertal female subject who begins menses during the study.

Effective and approved methods of contraception applicable for the subject and/or her/his partner are defined below:

- Progestogen-only oral hormonal contraception
- Cap, diaphragm, or sponge with spermicide
- Combination of male or female condom with cap, diaphragm, or sponge with spermicide

- Combined (estrogen- and progestogen-containing) oral, intravaginal, or transdermal hormonal contraception
  - Injectable or implanted hormonal contraception
  - Intrauterine devices
  - Bilateral tubal ligation or tube insert (such as the Essure system) at least 3 months before the study
  - Vasectomy at least 3 months before the study
4. Subject is willing and able to comply with all of the time commitments and procedural requirements of the clinical study protocol
  5. Fully understands and signs an informed consent form before any investigational procedure(s) are performed

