#### **8.4.5 Method of Assigning Subject to Treatment Groups: Randomization**

Upon an ICF signature by a given subject, a unique subject identification number (SIN) for that subject will be assigned via Electronic Data Capture (eDC). The eDC will be accessed immediately after ICF signature has been recorded by study center personnel. The SIN will be used for the whole duration of the study. This SIN will be allocated in ascending sequential order to each subject. Once a SIN has been assigned, that number must not be used again for any other subject (e.g., when a subject is withdrawn from the study, that subject's SIN must not be reused for any other subject, including resccreens).

Upon confirmation of eligibility for a given subject to participate in the study, a unique randomization number will be assigned to that subject via Interactive Response Technology (IRT). The randomization number for a given subject will be used to identify the treatment arm the subject will be assigned to.

Subjects will be randomized in a 2:1 ratio to receive 2 treatments of daylight photodynamic therapy (DL-PDT) with either MAL cream 16.8% (CD06809-41) or a vehicle cream. Randomization will be stratified by study centers using the Interactive Response Technology (IRT) System.

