#### 10.1.3.1 Primary Endpoint Analysis

The proportion of subjects with complete clearance of all AK lesions treated at 12 weeks after the last DL-PDT (Visit 6) will be analyzed using the Cochran-Mantel-Haenszel (CMH) test stratified by analysis center. The p-value for the treatment comparison (MAL DL-PDT vs. vehicle DL-PDT) will be calculated from the general association statistic of the stratified CMH test. Difference in proportions between treatment groups and the 99.875% confidence interval of the difference will be based on the large sample approximation method for binary data.

The hypothesis test for the primary efficacy endpoint will be evaluated on the ITT population at the two-sided significance level  $\alpha = 0.00125$ .

Efficacy will be claimed if the between treatment difference on the primary endpoint is statistically significant with a p-value  $< 0.00125$ .

This result will provide an acceptable level of evidence of efficacy, in presence of good internal consistency across primary and secondary endpoints in the absence of a second pivotal study.

For the primary analysis all subjects on the ITT population with missing data for the primary endpoint will be classified as non-responders regardless of treatment allocation.

---

---

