### 10.1.3.3 Secondary Endpoints Analysis

The percent reduction from baseline in the number of cleared treated lesions at 12 weeks after the last DL-PDT treatment (Visit 6) will be analyzed using an ANCOVA with treatment, analysis center and baseline AKs count as fixed effects; the difference in percent reduction between MAL DL-PDT and vehicle DL-PDT, the 99.875% confidence interval of the difference and the p-value will be generated from the ANCOVA model.

For analysis of percent reduction from baseline in the number of treated AK lesions, missing counts of cleared treated lesions for subjects on the ITT population will be imputed using MI (Multiple Imputation) under the Missing At Random (MAR) assumption. It is expected that the pattern of

---

missing data will be monotonic, with slight deviations being corrected by the Markov Chain Monte Carlo (MCMC) method of the MI procedure. Linear regression will be employed to model the missing lesion count data, with the following covariates included in the imputation model: treatment and non-missing data from earlier time points.

The proportion of subjects with 75% or greater reduction from baseline in the number of cleared treated lesions at 12 weeks after the last DL-PDT treatment (Visit 6) will be analyzed using the Cochran-Mantel-Haenszel (CMH) test stratified by analysis center. The p-value for the treatment comparison (MAL DL-PDT vs. vehicle DL-PDT) will be calculated from the general association statistic of the stratified CMH test. Difference in proportions between treatment groups and the 99.875% confidence interval of the difference will be based on the large sample approximation method for binary data.

For the analysis of proportion of subjects achieving a partial response, all subjects of the ITT population with missing data will be classified as non-responders regardless of treatment allocation.

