10.6.4 Statistical and Analytical Issues

10.6.4.1 Adjustment for Covariates

The analysis of percent reduction from baseline in the number of cleared treated lesions at 12 weeks after the last DL-PDT treatment (Visit 6) will use an adjustment for the number of baseline AK lesions as described in section 10.6.3.

No other adjustment for covariates is planned for the primary and secondary efficacy analyses.

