10.6.4.8 Examination of Subgroups

All subgroup analyses are exploratory in nature.

To determine whether the treatment effect is consistent across various subgroups, the estimate of the between-treatment effect (with nominal 99.875% and 95% CI) for primary endpoint and secondary endpoints will be presented within each category of the following classification variables:

- AK lesions location
 - ✓ Face
 - ✓ Balding scalp
- Baseline AK grade
 - ✓ Grade 1 (mild) AK
 - ✓ Grade 2 (moderate) AK
- Sex
 - ✓ Male
 - ✓ Female
- Number of baseline AK lesions
 - ✓ 4-8 AK lesions
 - ✓ 9-12 AK lesions

Statistical Analysis Plan

- Fitzpatrick skin type
 - ✓ Type I, II and III
 - ✓ Type IV, V and VI

Differences in proportions and their nominal 99.875% and 95% confidence intervals by category for the classification variables listed above will be reported as well as presented graphically (Forest plot) on the ITT population.

Missing data will be imputed using the same methods foreseen for the primary analysis of the primary endpoint and for the analysis of the secondary endpoints (see section 10.6.4.2).

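### The primary CMH test is valid and well powered as planned, but for no stated reason it leaves out baseline treated-lesion count; adjusting for it within center would bring a small precision gain (minor)

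*Protocol*

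**What the plan says.** Protocol 7.3 defines the primary endpoint as "subject complete response, defined as the proportion of subjects with complete clearance of all AK lesions treated" at Visit 6. Protocol 9.1.1 adds that one uncleared treated lesion makes the subject a non-responder. The number of lesions per subject varies threefold: "Subjects have at least 4 but no more than 12 clinically confirmed thin and moderately thick" (Protocol 8.3.2). Protocol 8.4.1.1 has lesions counted, and those to be treated selected, before the site requests the treatment assignment.

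Protocol 10.1.3.1 says the primary proportion "will be analyzed using the Cochran-Mantel-Haenszel (CMH) test stratified by analysis center". SAP 10.6.1 repeats this, and SAP 10.6.3 uses the same test for the 75% responder endpoint. SAP 10.6.4.1 adjusts the percent-reduction analysis for baseline count and then states: "No other adjustment for covariates is planned for the primary and secondary efficacy analyses".

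The count is used in three other places:
- The first secondary endpoint is analyzed by "ANCOVA with treatment, analysis center and baseline AKs count as fixed effects" (Protocol 10.1.3.3).
- SAP 10.6.4.8 shows the treatment effect on the primary endpoint within bands of 4-8 and 9-12 lesions, as an exploratory analysis.
- SAP 10.2.3 summarizes count and count band by arm.

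On allocation, Protocol 8.4.5 says: "Randomization will be stratified by study centers using the Interactive Response Technology (IRT) System".

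**The concern.** At a given per-lesion clearance probability, clearing 12 lesions out of 12 is harder than clearing 4 out of 4. The count is therefore expected to be prognostic because of how the endpoint is built. It is already collected, it precedes assignment, and the same SAP treats it as a covariate worth using for the percent-reduction endpoint. The test that carries the efficacy claim does not use it.

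What is at stake is efficiency. The trial relies on one comparison at two-sided 0.00125 in place of a second pivotal study, and Protocol 8.2.1 wants power to hold up if the true rates differ from those assumed. A prognostic covariate that costs no extra data would narrow the interval and add some power if the effect were smaller than planned. It would also take account of any chance difference in count between arms, through a rule set before unblinding.

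**Working it through.** **The plan's own figures.** Inputs from Protocol 10.2: 380:190 randomized, 45% v 15%, alpha 0.00125 (two-sided per Protocol 10.1.3.1), 7% non-evaluable. A two-proportion normal approximation with pooled null variance on 93% of subjects gives power of 99.999%. Scoring the 7% as failures among all 570 gives 99.997%. The stated power of more than 90% is met. Ninety per cent power needs only 213 evaluable subjects, and 213/0.93 rounds up to 230. N = 570 comes from the long-term follow-up target: 380 x 0.93 x 0.45 x 0.70 x 0.90 = 100.2 MAL subjects. With 93% evaluable, 90% power extends down to a difference of about 18 points from a 15% vehicle rate.

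**How strongly count predicts response.** The documents give neither the count distribution nor the correlation between a subject's lesions. Assumed here: counts uniform on 4-12, and beta-binomial clearance calibrated to 45% and 15% overall. At 4 and 12 lesions respectively:
- Correlation 0: MAL 66% and 29%; vehicle 35% and 4%.
- Correlation 0.4: MAL 54% and 39%; vehicle 23% and 11%.

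**Ceiling on the gain at 45% v 15%.** The unadjusted SE is sqrt(0.45 x 0.55/353.4 + 0.15 x 0.85/176.7) = 0.0377, where 353.4 and 176.7 are 93% of each arm. Full conditioning on count gives 0.0364 at correlation 0 (variance efficiency +7.2%), 0.0374 at 0.3 (+1.6%) and 0.0376 at 0.5 (+0.7%). With counts skewed low or high, the largest gains are 6.1% and 5.1%.

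**Gain from linear covariance adjustment within center.** Simulation: 38 centers x 15 = 570, 2:1 in blocks of 3, 7% missing scored as failure, 1,500 replicates. Ratio of squared mean z, adjusted to CMH:

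| Rates | Corr. 0 | 0.1 | 0.2 | 0.4 |
|---|---|---|---|---|
| 45% v 15% | 1.049 | 1.026 | 1.016 | 1.005 |
| 30% v 15% | 1.064 | 1.033 | 1.018 | 1.009 |

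A repeat with and without center effects gave gains of 0.6-5% and 0.5-6%, with null rejection close to nominal. In subjects, the table spans 570 x 0.005 = 3 to 570 x 0.064 = 36.

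**What the gain means.** At 45% v 15% with all 570 subjects, the SE is sqrt(0.45 x 0.55/380 + 0.15 x 0.85/190) = 0.0364, and the 99.875% half-width is 3.227 x 3.64 = 11.7 points. Dividing by sqrt(1.005) to sqrt(1.049) gives 11.7 to 11.5, a gain of 0.03 to 0.28 points. Power is about 1 either way. At 30% v 15%, power rises from 0.70-0.72 to 0.72-0.75 in the tabulated simulation. The repeat put the rise at about 0.4 to 5 points.

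**Chance imbalance.** The SD of a uniform count on 4-12 is sqrt(80/12) = 2.58. The SE of the arm difference in mean count is 2.58 x sqrt(1/380 + 1/190) = 0.23 lesions. The average slopes above run from (23 - 11)/8 = 1.5 to (66 - 29)/8 = 4.6 points per lesion. A one-SE imbalance therefore moves the estimate by about 0.3 to 1.1 points.

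**Crossing count with center.** Replacing center strata by center x (4-8/9-12) strata gave squared-z ratios of 0.94-0.98. In a second layout (40 centers, 4,000 runs, 33% v 15%), power fell from 86.7% to 84.8% at correlation 0, and from 85.7% to 82.8% at 0.3.

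**The case against.** The strongest reply is that nothing is broken. Randomization is stratified by center, the CMH strata follow that factor with small centers pooled, and a center-stratified randomized comparison is valid without the count. SAP 10.6.4.1 shows that covariates were considered and a choice made. At the design rates no decision turns on a quarter of a point of interval half-width, and 30% v 15% is not a planning scenario. The upper gains need independent lesions. That is the least plausible case, because a subject's lesions share the same skin, the same cream application and the same daylight session. All of this stands, and it sets the priority.

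It does not remove the point. Matching the randomization stratum does not prevent adding a baseline covariate within it, and the gain, though small, was positive in every non-null scenario simulated.

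Three stronger readings are tempting, and the documents do not support them:
- A reader might infer that the omission has no rationale at all. The documents state none, but following the randomization stratum is a recognized design-based one.
- A reader might infer that chance imbalance in count biases the primary result. Such imbalance is part of the sampling variation that the test and interval already allow for, and it would be visible in the SAP 10.2.3 summaries.
- A reader might infer that the trial is underpowered. At 45% v 15% it is not.

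**Conclusion.** The point holds as a minor efficiency improvement. The planned analysis omits a covariate that the endpoint definition makes prognostic and that the SAP uses elsewhere, and it gives no reason. Adjusting within center would improve efficiency by about 0.5-5% at 45% v 15%, where only interval width benefits. At 30% v 15% the gain is about 0.5-6%, or 0.4 to 5 points of power.

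These sizes rest on uniform counts, a within-subject correlation of 0 to 0.4, and equal-sized centers. With strong correlation the gain nearly vanishes. The gain for the 75% responder endpoint was not simulated.

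**What to change.** In Protocol 10.1.3.1 and 10.1.3.3 and SAP 10.6.1, 10.6.3 and 10.6.4.1:

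1. Keep analysis center as the stratum. Do not cross it with count bands.
2. Prespecify a randomization-based linear covariance adjustment of the center-stratified risk difference for baseline number of treated lesions. It gives the p-value, the difference and the 99.875% interval from one method. A conditional logistic model stratified by center would not, because it eliminates the center intercepts and cannot itself yield a standardized risk difference.
3. Apply the same method to the 75% responder endpoint.
4. Keep the unadjusted center-stratified CMH as a sensitivity analysis.

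No new data are needed, and the target remains the risk difference. The cost is a change to both protocol and SAP text before database lock. SAP section 11 sends changes to principal features that arise from the blind review to a protocol amendment, and the primary test is such a feature. The multiple-imputation pooling and tipping-point analysis in SAP 10.6.4.2 would have to run on the adjusted statistic.

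If the sponsor prefers not to change the primary test, prespecify the adjusted analysis as supportive. That keeps it from being a post hoc response to an observed imbalance.
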